## STUDY MANAGEMENT

### SCHEMA

Use of an intravenous fish oil emulsion in infants with cholestasis

DESIGN Observational, compassionate use, single cohort study

DURATION Open

SAMPLE SIZE 25

POPULATION Infants less than 12m of age at time of recruitment

STRATIFICATION (*as required*) N/A

REGIMEN OR INTERVENTION (*as required*) N/A

SUBSTUDIES (*as required*) N/A

Version date 1/12/2018

## 1.0 HYPOTHESIS AND STUDY OBJECTIVES

### 1.1 Hypothesis

Use of omegaven in infants with cholestasis will be temporally related to resolution of cholestasis.

### 1.2 Primary Objective(s)

The aims of the study are to assess the effect of intravenous fish oil emulsion (omegaven™) in place of the currently used intravenous soybean oil lipid emulsion (Intralipid™) in subjects with short bowel syndrome and cholestasis or with PNALD (parenteral nutrition associated liver disease).

## 2.0 INTRODUCTION

### 2.1 Background

Functional short gut (or short bowel syndrome, SBS) is defined as the inability to tolerate all nutritional requirements via the enteral route, and a continuing dependence of partial or complete parenteral nutrition.

Development of SBS (short bowel syndrome) is more common in newborn infants than at any other age group, and may result from gastroschisis, gastrointestinal atresia, intestinal volvulus, or necrotizing enterocolitis. Treatment is aimed at:

1. Nutritional support, through the use of parenteral nutrition.
2. Gut rehabilitation and adaptation through gradual introduction and advancement of enteral feeds.
3. Prevention of secondary problems (e.g. bile acid deficiency or bacterial overgrowth).
4. Prevention of complications (e.g. cholestasis).

Concerted, coordinated management, including parenteral nutrition, has greatly improved the survival and quality of life of subjects with SBS. However, prolonged use of parenteral nutrition is not without risk. Parenteral nutrition associated cholestasis (PNAC); also know as parenteral nutrition associated liver disease (PNALD) or intestinal failure associated liver disease (IFALD); is one of the leading causes of death in SBS.

The causes of PNALD are unclear, but may include:

1. Absence of enteral feeds.
2. "Toxic" components in parenteral nutrition (e.g. aluminium, phytosterols, methionine, tryptophan).
3. Lack of certain beneficial nutrients in parenteral nutrition (e.g. serine, choline).

In recent years, much attention has been paid to the effect of parenteral lipid on PNAC. In the US, parenteral lipids are vegetable-based. Most widely used is Intralipid™ with is

Version date 1/12/2018

a mixture of soybean oil and egg phospholipids. Although it has a generally excellent short- and long-term safety record, there are concerns about its long term use. As it is vegetable based it contains relatively high amounts of phytosterols (cholesterol-like lipids derived from plants). In adults and children with SBS and PNAC, serum levels of phytosterols correlate with the degree of hepatic and biliary dysfunction.

Omegaven is a fish-oil derived intravenous lipid emulsion that is not licensed in the US, but is widely used in Europe. It differs in composition from intralipid in many ways, for example it is much higher in omega-3 fats, lower in omega-6 fats, and contains no phytosterols.

### Composition of Different iv lipid emulsions (from Puder 2009)

**TABLE 1.** Comparison and Characteristics of Parenteral Lipid Emulsions (100 g fat/L)

Product	Intralipid	Liposyn II	Omegaven
Manufacturer	Fresenius Kabi	Hospira	Fresenius Kabi
Oil source (g)			
Soybean	100	50	0
Safflower	0	50	0
MCT	0	0	0
Olive oil	0	0	0
Fish	0	0	100
Fat composition (%)*			
Linoleic	50	65	0.4
$\alpha$ -Linolenic	9	4	<0.2
EPA	0	0	2.1
DHA	0	0	2.3
Oleic	26	17.7	1.0
Palmitic	10	8.8	0.6
Stearic	3.5	3.4	0.1
Arachidonic	0	0	0.3

[figure not shown]
There are an increasing number of case-control studies suggesting significant clinical benefits to the use of omegeaven in established PNALD in infants (Gura 2006, Gura 2008, Diamond 2009, Puder 2009).

The largest of these published cohorts is that of Puder, from Boston Children's Hospital (see attached file). In that study 42 infants who developed PNALD on standard intravenous lipid emulsions were given omegeaven, and compared to 49 historical controls. Subjects were eligible for omegeaven if they had cholestasis (direct bilirubin  $\geq$  2 mg/dL), were likely to be on parenteral nutrition at least 30d, and had acquired or congenital GI disease. Subjects with cystic fibrosis, metabolic disorders or hepatitis C were excluded. They were compared to historical controls who had two consecutive direct bilirubin measurements  $\geq$  2 mg/dL. Omegeaven was given at a dose of 1 g/kg/d, and intralipid at 1-4 g/kg/d (depending on attending preference and lipid tolerance). The fish oil group were generally more sick at study entry than the historical controls, they had been on parenteral nutrition longer (63d vs. 40d,  $p=0.008$ ) and their direct bilirubin was higher (5.5 vs. 3.3,  $p=0.0003$ ). Despite these baseline differences, the fish oil group had a steady and sustained fall in direct bilirubin and ALT, while these measures continued to increase in the historical controls.

Version date 1/12/2018

**Figure** Direct bilirubin and ALT in the fish oil group, and the historical controls (from Puder 2009).

Cholestasis resolved in 45% (19/42) of the fish oil group while still on PN, compared to 4% (2/46) of the historical cohorts.

The rate of the combined outcome of death or required liver transplant was significantly lower in the fish oil group (9.5%) than in the historical controls (34.7%,  $p=0.0005$ ). The crude rate of reversal of cholestasis in subjects who did not die or require liver transplants was 8.6x greater in the fish oil group than in the historical controls. This increased to 17.4x higher rate once differences in baseline characteristics were accounted for.

The main safety measures followed (hypertriglyceridemia, and coagulopathy) significantly favored the fish oil group.

Version date 1/12/2018

[figure not shown]
**Table** Incidence of hypertriglyceridemia and coagulopathy in fish oil group, and the historical controls (from Puder 2009).

**TABLE 3.** Safety of Fish Oil From Baseline Until the End of Follow-Up\*

Safety Marker	Fish Oil (n = 42)	Soybean Oil (n = 49)	P
Triglycerides (mg/dL), mean $\pm$ SD †	105	166	0.0002
Hypertriglyceridemia (>400), rate (weeks of observation)	0.3	8.8	0.0003
INR, mean †	1.2	1.6	0.004
INR >2, rate (weeks of observation) ‡	1.5	3.6	0.08
Platelets, mean †	192	174	0.44
T/T ratio, mean †	0.032	—	—
T/T ratio >0.2, rate (weeks of observation) ‡	0.5	—	—

Although there was no significant difference in INR between the groups over the entire study, INR began to increase in the controls near the end of the study as they developed worsening end-stage liver disease. In the fish oil group, INR remained low during the entire study.

**Figure** INR in the fish oil group, and the historical controls (from Puder 2009).

### 3.0 STUDY DESIGN

Compassionate use, single cohort, observational study.

### 4.0 SELECTION AND ENROLLMENT OF SUBJECTS

#### 4.1 Inclusion Criteria

Infants on parenteral nutrition who have congenital or acquired gastrointestinal diseases that place them at risk of short bowel syndrome (SBS) or prolonged parenteral-nutrition-dependence, will be considered eligible for the study if either (1) they remain cholestatic (bilirubin > 2 mg/dL) after 4wks of reduced lipids and trace elements, or (2) If their direct bilirubin is > 6 mg/dL in the absence of suspected or proven infection.

#### 4.2 Exclusion Criteria

Subjects will be considered ineligible for the study if they are felt unlikely to survive more than 30d, or unlikely to require parenteral nutrition for at least 30d.

#### 4.3 Study Enrollment Procedures

Clinical nutrition rounds, between the PI and the NICU dietician, occur every 1-2wk as part of the routine clinical care of the infants. As part of the clinical care of the infants, and infant identified as having cholestasis or PNALD (direct bilirubin  $\geq$ 2 mg/dL on two consecutive occasions  $\geq$ 8d apart) have their intralipid infusion rate reduced to 1 g/kg/d and have the trace elements added to their parenteral nutrition reduced. The current protocol will not alter this.

### 5.0 STUDY TREATMENT (*OR INTERVENTION*)

#### 5.1 Regimens (*or Intervention*), Administration, and Duration

The intervention is the use of omegaven (an intravenous fish oil emulsion) in place of intralipid (the currently used soybean oil intravenous lipid emulsion, until parenteral nutrition is discontinued, or until cholestasis resolves.

Parents of eligible patients will be approached for consent for their infants to take part in the study. If they agree, the PI will contact the FDA to receive an IND number for the infant (copies of the required FDA paperwork will be sent to the IRB). Omegaven will be ordered from the manufacturer. Once the IND number is received, the IRB will be informed of the subjects IND number. Once the IND number is received, and communicated with the IRB, and the omegaven is received, intralipid infusions will be

Version date 1/12/2018

stopped and omegaven will be infused at the rate of 1 g/kg/d. Clinically-indicated labs will be monitored, as for all patients on prolonged parenteral nutrition, i.e. CBC, electrolytes, BUN, Creatinine, ALT, AST, Alkaline phosphatase, albumin, total bilirubin, direct bilirubin and serum triglycerides will be measured at least every 2 weeks. No additional labs will be required as part of the study.

#### Adjustment of Omegaven Dosage

Hypertriglyceridemia: If serum triglycerides are > 400, other causes will be excluded (e.g. renal disease, medications). If no other causes can be found, the clinical team caring for the baby may decide to reduce the infusion of omegaven by 25%, depending on their clinical assessment of risk and benefits.

Essential Fatty Acid Deficiency: If there are concerns that essential fatty acid deficiency may be occurring (characteristic skin rash plus unexplained thrombocytopenia), the clinical team caring for the baby may decide to discontinue omegaven and re-start infusion of intralipid at a rate of 0.5 – 1 g.kg/d.

Other: The clinical team caring for the baby will be allowed to withhold the omegaven infusion or restart the intralipid infusion for any reason if they believe that to be in the best interests of the patient.

#### Discontinuation of Omegaven

Omegaven will be discontinued either (1) once parenteral nutrition is discontinued, irrespective of the direct bilirubin level, or (2) once the direct bilirubin has been below 2 mg/dL for more than 2 weeks. In the later case, if the direct bilirubin rebounds above 2 mg/dL at anytime the omegaven can be restarted. If omegaven is re-started, the discontinuation criteria will be the same as before: i.e. it will be discontinued when parenteral nutrition is discontinued or when the direct bilirubin has been below 2 mg/dL for more than 2 weeks.

#### Safety Assessment

Routine clinical labs will be used to monitor for the principal side effects of omegaven (thrombocytopenia, hypertriglyceridemia), and the response to treatment (direct bilirubin, ALT). INR and triene:tetrene ratio will be assessed as clinically indicated if coagulopathy or essential fatty acid deficiency are suspected.

### 5.2 Study Product Formulation and Preparation

Omegaven intravenous lipid emulsion as supplied by the manufacturer.

### 5.3 Pharmacy: Product Supply, Distribution, and Accountability

#### 5.3.1 Study Product Acquisition

Parents of eligible patients will be approached for consent for their infants to take part in the study. If they agree, the PI will contact the FDA to receive an IND number for the infant (copies of the required FDA paperwork will be sent to the IRB). Omegaven will be ordered from the manufacturer. Once the IND number is received, the IRB will be

Version date 1/12/2018

informed of the subjects IND number. Once the IND number is received, and communicated with the IRB, and the omegaven is received, intralipid infusions will be stopped and omegaven will be infused at the rate of 1 g/kg/d.

### 5.3.2 Study Product Accountability

The FDA permits the cost of omegaven to be billed to insurance carriers, or to public insurance. These costs will be largely, but not completely offset by the reduction in cost as the standard intravenous lipid (intralipid) will not be given. No additional laboratory tests will be carried out. If the relevant private or public insurance provider refuses to cover the additional cost of omegaven (approx \$50-75/d) we would expect that costs will be absorbed by either the UCDMC pharmacy. In the unlikely event that this does not prove possible, and alternative coverage for omegaven can not be found (e.g. internal NICU funds) the parents will be asked to pay for omegaven. The IRB will be informed of this eventuality should it occur. The consent form will clearly state the plans regarding charging for omegaven, and that the family would be payers of last resort if alternative methods of funding the omegaven are not successful.

### 5.4 Concomitant Medications

#### 5.4.1 Required Medications

Current receipt of parenteral nutrition (including iv lipids), are required for the diagnosis of PNALD, and therefore for enrollment in the study

#### 5.4.2 Prohibited Medications

None

#### 5.4.3 Precautionary Medications

None

## 6.0 CLINICAL AND LABORATORY EVALUATIONS

Version date 1/12/2018

## 6.2 Timing of Evaluations

### 6.2.1 Screening and Pre-Entry Evaluations

Clinical nutrition rounds, between the PI and the NICU dietician, occur every 1-2wk as part of the routine clinical care of the infants. As part of the clinical care of the infants, and infant identified as having cholestasis or PNALD (direct bilirubin  $\geq 2$  mg/dL on two consecutive occasions  $\geq 8$ d apart) are identified.

### 6.2.2 Entry Evaluations

Clinical nutrition rounds, between the PI and the NICU dietician, occur every 1-2wk as part of the routine clinical care of the infants. As part of the clinical care of the infants, and infant identified as having cholestasis or PNALD (direct bilirubin  $\geq 2$  mg/dL on two consecutive occasions  $\geq 8$ d apart) have their intralipid infusion rate reduced to 1 g/kg/d and have the trace elements added to their parenteral nutrition reduced. The current protocol will not alter this. If they remain cholestatic (bilirubin  $> 2$  mg/dL) after 4wks of reduced lipids and trace elements, or (2) if their direct bilirubin is  $> 6$  mg/dL in the absence of suspected or proven infection they will be considered eligible for the study.

### 6.2.3 Post-Entry Evaluations

Will continue as part of the clinical nutrition rounds

### 6.2.4 Discontinuation Evaluations

Will continue as part of the clinical nutrition rounds. Omegaven will be discontinued either (1) once parenteral nutrition is discontinued, irrespective of the direct bilirubin level, or (2) once the direct bilirubin has been below 2 mg/dL for more than 2 weeks. In the later case, if the direct bilirubin rebounds above 2 mg/dL at anytime the omegaven can be restarted. If omegaven is re-started, the discontinuation criteria will be the same as before: i.e. it will be discontinued when parenteral nutrition is discontinued or when the direct bilirubin has been below 2 mg/dL for more than 2 weeks. Omegaen may also be discontinued at any time is desired by the family, the attending physician or the study PI.

## 7.0 CLINICAL MANAGEMENT ISSUES

### 7.1 Toxicity

Routine clinical labs will be used to monitor for the principal side effects of omegaven (thrombocytopenia, hypertriglyceridemia), and the response to treatment (direct bilirubin, ALT). INR and triene:tetrene ratio will be assessed as clinically indicated if coagulopathy of essential fatty acid deficiency are suspected. If serum triglycerides are  $> 400$ , other causes will be excluded (e.g. renal disease, medications). If no other causes can be found, the clinical team caring for the baby may decide to reduce the infusion of omegaven by 25%, depending on their clinical assessment of risk and benefits. If there are concerns that essential fatty acid deficiency may be occurring

Version date 1/12/2018

(characteristic skin rash plus unexplained thrombocytopenia), the clinical team caring for the baby may decide to discontinue omegaven and re-start infusion of intralipid at a rate of 0.5 – 1 g/kg/d.

An external Data Safety Monitor ([name], Professor of Pediatrics, Section of Neonatology, Department of Pediatrics, Baylor College of Medicine and Texas Children's Hospital, Houston, TX) will be informed of all subjects recruited to the protocol. He will be informed, by e-mail, of any laboratory results on the subjects at least monthly, or within 7d of any significant change in biochemical data. He will have the authority to withdraw a subject from the protocol at any time. He will be unaware of the subjects name, but will be made aware of any pertinent clinical data relevant to lab interpretation (e.g. presence or absence of infection, underlying GI diagnosis, amount of enteral feeds etc). Subjects will be identified by an anonymous number when communicating with the external safety monitor.

#### 7.2 Other Diseases

N/A

#### 7.3 Pregnancy

N/A

#### 7.4 Breast-feeding (if applicable)

N/A

### 8.0 CRITERIA FOR DISCONTINUATION

#### 8.1 Permanent Treatment Discontinuation

Omegaven will be discontinued either (1) once parenteral nutrition is discontinued, irrespective of the direct bilirubin level, or (2) once the direct bilirubin has been below 2 mg/dL for more than 2 weeks. In the later case, if the direct bilirubin rebounds above 2 mg/dL at anytime the omegaven can be restarted. If omegaven is re-started, the discontinuation criteria will be the same as before: i.e. it will be discontinued when parenteral nutrition is discontinued or when the direct bilirubin has been below 2 mg/dL for more than 2 weeks.

#### 8.2 Premature Study Discontinuation

As for 8.1

### 9.0 STATISTICAL CONSIDERATIONS

#### 9.1 General Design Issues

This is a compassionate use, non-hypothesis testing protocol. Summary descriptive statistics will be generated, e.g. time to resolution of cholestasis.

Version date 1/12/2018

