## 9.2 Endpoints

### 9.2.1 Primary Endpoints (including definitions)

Time to resolution of cholestasis (direct bilirubin < 2 mg/dL without subsequent rebound above 2 mg/dL).

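### The only endpoint is a time to event, but no rule covers infants with no observed resolution time, so a plain summary of observed times would describe only successes

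*Combined protocol and SAP*

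**What the plan says.** Section 9.2.1 defines the one endpoint: "Time to resolution of cholestasis (direct bilirubin < 2 mg/dL without subsequent rebound above 2 mg/dL". Section 9.2.2 lists no secondary endpoints. On analysis, section 9.1 says the protocol tests no hypothesis and then: "Summary descriptive statistics will be generated, e.g. time to resolution of cholestasis". Section 9.5 Analyses only refers back. No section gives a time origin, an estimator, a denominator or a censoring rule.

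On follow-up, the Schema has "DURATION Open", and section 6.2.3 says of evaluations after entry: "Will continue as part of the clinical nutrition rounds". Section 5.1 sets bilirubin at least every 2 weeks, as for patients on prolonged PN, and adds no study labs. No bilirubin schedule is given for the time after PN ends.

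On stopping, section 8.1 ends omegaven "once parenteral nutrition is discontinued, irrespective of the direct bilirubin level", or after more than 2 weeks below 2 mg/dL. In the second case, "if the direct bilirubin rebounds above 2 mg/dL at anytime the omegaven can be restarted" (section 5.1, Discontinuation of Omegaven).

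**The concern.** A mean or median of observed times can be computed only for infants who have a time. The plan leaves at least three groups without one:

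- infants whose PN ends while they are cholestatic and whose bilirubin is not measured again;
- infants who die or are transplanted;
- infants still cholestatic when the data are analysed.

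If they are left out, the trial's only result is conditional on success, and readers would take it as the experience of everyone treated.

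Rebound adds a narrower gap. Section 9.2.1 requires that no rebound follows, but not how long it is looked for, whether the clock runs on to a later sustained fall after a restart, or how a last value below 2 mg/dL with nothing after it counts. Two analysts could date resolution differently from the same labs.

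**Working it through.** **Inputs from the documents.** Up to 25 infants (section 9.4). In the published fish oil cohort described in section 2.1, 19 of 42 resolved while on PN, and 9.5% died or needed a transplant. **Assumed, not in the documents:** constant hazards; random censoring; 90%, 75% or 45% observed to resolve; a resolvers-only median of 8 weeks (step 4); a true median of 12 weeks (steps 3 and 5).

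**1. The plan's own figures.** 19/42 = 45.2%, matching the stated 45% (exact 95% CI 29.8% to 61.3%). 4/42 = 9.5%, matching the stated rate. The 25 has no derivation, so it can be neither reproduced nor refuted.

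**2. Will some infants lack a time?** At 19/42, 25 × 0.452 = 11.3 infants would have a time on PN and 13.7 would not. Even if 90% resolve, the chance of at least one without a time is 1 − 0.90^25 = 93%.

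**3. Error in a resolvers-only median.** Let resolution have hazard λ and censoring hazard μ, so the share observed to resolve is p = λ/(λ+μ). Times among resolvers then have hazard λ+μ and median ln2/(λ+μ). The median without censoring is ln2/λ. The ratio is (λ+μ)/λ = 1/p: 1.11 at 90%, 1.33 at 75%, 2.21 at 19/42.

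With an assumed true median of 12 weeks, the resolvers-only median is 10.8, 9.0 or 5.4 weeks. If censoring comes instead from one fixed cut-off, the resolvers-only median is −ln(1 − p/2)/λ: 10.3, 8.1 or 4.4 weeks. In 4,000 simulated cohorts of 25 under random censoring, a Kaplan-Meier median was typically 12.0 to 12.1 weeks, and was reached in 97% of runs at the lowest share.

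**4. The same point as a cumulative incidence.** Let H = ln2/8 per week be the total hazard, and d = 4/42 the share who die or are transplanted, as a competing event. Among resolvers only, the share resolved by 12 weeks is 1 − exp(−12H) = 64.6%. Among all treated, the cumulative incidence is p/(p+d) × [1 − exp(−(p+d) × 12H)]:

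| Share resolving | Resolved by 12 weeks, all treated |
|---|---|
| 90% | 0.904 × 0.645 = 58.3% |
| 75% | 0.887 × 0.585 = 51.9% |
| 19/42 | 0.826 × 0.434 = 35.9% |

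Expected numbers still at risk are 25 × exp(−12H) = 8.8 at 12 weeks and 25 × exp(−26H) = 2.6 at 26 weeks. Precision at full size is limited: 11/25 = 44% (95% CI 24% to 65%); 19/25 = 76% (55% to 91%).

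**5. Can the direction reverse?** Keep the true median at 12 weeks and let the chance of being unobserved depend on resolution time through a logistic curve centred at 12 weeks with a scale of 4 weeks. If slow resolvers are the ones missed, the observed median is 5.1 weeks. If fast resolvers are missed, for example weaned from PN before bilirubin falls and then not measured, it is 22.7 weeks.

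**The case against.** The strongest reply is that this is a compassionate-use cohort of at most 25, expressly not testing a hypothesis, and that descriptive statistics can include a Kaplan-Meier or cumulative incidence curve. That is fair. A reader might infer that the plan commits to summarising resolvers only; it does not, and its wording leaves other summaries open. What stands is that nothing commits to a method that keeps the other infants in, and a descriptive figure still needs a denominator.

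Three other tempting readings go too far.

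- **That rebound has no rule.** Section 9.2.1 has one: a fall followed by rebound is not resolution. Only the window, the timing of a later fall and unconfirmed last values are open.
- **That every early stop loses the outcome.** The clinical team "will be allowed to withhold the omegaven infusion or restart the intralipid infusion for any reason" (section 5.1), and omegaven "may also be discontinued at any time is desired by the family, the attending physician or the study PI" (section 6.2.4). But the endpoint is not tied to being on omegaven. Such an infant may stay on PN with bilirubin at least every 2 weeks, and evaluations continue on nutrition rounds.
- **That the summary must be too short.** Step 5 shows the opposite is possible, and a route to it exists because PN can end before bilirubin clears.

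Section 4.2 also excludes infants thought unlikely to survive more than 30 days or to need PN for at least 30 days. That reduces early death and early PN exit but does not remove them. Finally, the 1/p factors treat death and transplant as censoring, so they do not describe a competing-risks median exactly.

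**Conclusion.** The point holds and should be fixed. The analysis of the only endpoint is under-specified, and its plainest reading, a mean or median of observed times, covers resolvers only. Infants without a time are very likely even if 90% resolve.

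The usual effect is a summary that is too short, by a factor of about 1.1 to 2.2 as the share resolving falls from 90% to 45%. Those factors are illustrative. They rest on constant hazards and random censoring, and the 45% is an on-PN rate from another cohort that may understate eventual resolution. The 12-week figures further assume the 8-week median and that no infant both resolves and later dies or is transplanted. The documents do not fix the direction or size of the error for this trial. They do show that no rule controls it.

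**What to change.** In sections 9.1 and 9.5 Analyses, state:

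- **Population and origin:** all infants who receive any omegaven, from first infusion.
- **Results:** the number resolved out of all treated; the number who died or were transplanted; and the cumulative incidence of resolution (Aalen-Johansen), with death and transplant as competing events, a 95% CI and numbers at risk, at a prespecified early time such as 12 weeks. Give later times only if enough infants remain at risk, and a median only if reached.
- **Dating:** resolution is the first direct bilirubin below 2 mg/dL not followed by a value above 2 mg/dL up to a stated data cut-off. An infant who rebounds stays unresolved until a later fall meets the same rule. Report how many resolutions have no later confirming value.
- **Follow-up and censoring:** use clinically obtained bilirubin values after omegaven stops or intralipid restarts. Censor unresolved infants at their last direct bilirubin. Report how many were censored when PN or follow-up ended, because that censoring may be informative.
- **Measurement:** labs about every 2 weeks fix the resolution date only to within an interval.

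The cost is a few lines of text and standard software, with no new labs and no hypothesis test. Intervals will be wide with at most 25 infants, the headline figure will probably look less favourable, and resolution after PN will be seen only where labs were drawn for clinical reasons.
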